### Sample size

We require a minimum of 342 DMPA clients randomized to receive care from either the LHV or an LHW (1:1 allocation) for 90% power and 5% significance level to test the non-inferiority hypothesis that LHWs can screen potential DMPA clients for method initiation just as adequately as LHVs with a non-inferiority margin of 7.5%, assuming that both LHVs and LHWs perform at a 95% success rate. In Pakistan, there is usually at least one LHV assigned to a health facility and many more LHWs affiliated with and under the supervision of resident LHVs. Therefore, we will use a 3 to 1 ratio of LHWs to LHVs at each health facility in the trial. The three LHWs will be placed on rotation to cover a three-month enrollment and data collection period in the health facility. Rotations among the three LHWs will be based on their individual availability and schedules; not on their perceived competencies or the preference of facility staff.

In order to meet the desired sample size from LHWs and LHVs, we will select 10 health facilities that provide the most DMPA in Karachi and Thatta districts. These facilities will be distributed between rural and urban areas. For logistical reasons, we plan to obtain the full target sample size of 342 DMPA initiators from the urban health facilities to ensure that adequate analyses can be done with this group. We will recruit additional participants from rural facilities to help assess possible differences in performance between LHVs and LHWs in rural and urban areas. Although, we don't expect these differences to exist, the additional sample size will help us to assess whether differences may be likely to exist. If we can be comfortable that providers in rural and urban areas perform in similar manner, the overall sample size for the analysis may be pooled for an increase in power. Please note, however, that the additional sample size from rural areas will not be adequate for separate analyses by location or to assess rural and urban differences statistically. Rural facilities will likely provide a much lower number of DMPA acceptors in the three-month data collection period, but they will each be selected for their ability to enroll at least 20 new acceptors in that period of time. We will then expect to enroll approximately 100 DMPA acceptors from the rural facilities in the recruitment period for an overall total sample size of approximately 442 for this study.

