We require a minimum of 342 DMPA clients randomized to receive care from either the LHV or an LHW (1:1 allocation) for 90% power and 5% significance level to test the non-inferiority hypothesis that LHWs can screen potential DMPA clients for method initiation just as adequately as LHVs with a non-inferiority margin of 7.5%, assuming that both LHVs and LHWs perform at a 95% success rate. In Pakistan, there is usually at least one LHV assigned to a health facility and many more LHWs affiliated with and under the supervision of resident LHVs. Therefore, we will use a 3 to 1 ratio of LHWs to LHVs at each health facility in the trial.

For logistical reasons, we plan to obtain the full target sample size of 342 DMPA initiators from the 5 urban health facilities in Karachi to ensure that adequate analyses can be done with this group. We will recruit additional participants (~100) from 5 rural facilities in Thatta to help assess possible differences in performance between LHV and LHWs in rural and urban areas, but the expectation is that there will be no difference. LHWs undergo standardized training in Pakistan. If we can be comfortable that providers in rural and urban areas perform in similar manner, the overall sample size for the analysis may be pooled for an increase in power. The decision whether to pool the data or not will be made during the blind review of the data as described below.

Given the relationship between LHWs and LHV within clinics, we plan to account for the correlations of participant outcomes within providers and providers within clinics in the analysis. We expect that some of these correlations would lead to decreases in power and others to lead to increases in power for within clinic comparisons. Power calculations were not adjusted for these potential correlations as the net effect on power may be offset with each other.

V. General Analytic Considerations

A. Data Sources

A.1 Client exit interview

Client exit interviews measure the study's secondary outcomes of client satisfaction with the method and provider. The exit interview also provides additional information related to appropriate screening such as discussion of side effects, warning/danger signs, advantages and disadvantages of DMPA use with clients. The client exit interview includes questions on the following domains:

1. Sociodemographic characteristics
2. Experiences using contraceptive methods
3. Factors in her decision to use DMPA

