Even though the study is open labeled, the randomization was prepared by an independent randomization manager and data management is separated from the analysis team. Thus, the analysis team will initially be blinded to the group assignments. Unblinding of the analysis team will follow a three-step process: First, key decisions regarding the primary and secondary outcomes listed above will

be made blinded to study group assignment. These outcome variables will be constructed, checked for missing data, distributional anomalies or other problems, finalized and verified. Decisions about re-categorization, transformation, missing data, and final variable definition will be completed after initial descriptive analysis and prior to further analysis for the specific objectives. Descriptive analysis of the outcomes will be done by facility and rural/urban designation. This check will also include a check of protocol violations, such as randomization errors (this review will be coordinated between the data manager and the randomization manager to maintain blinding of the analysis team) to decide if any data should be excluded from the analysis. Primary analysis will be conducted based on the intent to treat (ITT) approach where all participants randomized will be analyzed in the study group to which they were randomized. During blind review, decisions will be made regarding any modification to the ITT principle for primary analysis and whether a per protocol analysis will be conducted as secondary or sensitivity analysis. Second, once these key decisions have been made, the randomization manager will provide a participant list with blinded study arm assignments to the analysis team. A descriptive bivariate analysis will be done using blinded treatment assignments stratified by rural/urban designation to assess whether pooling the data will be appropriate. A decision whether further analysis will be pooled or not will be done at this time. Partial blinding will be maintained until statistical conclusions regarding the primary outcome (screening outcome) and primary analysis have been made and verified. This will be based on the pooled data or on the urban data only depending on the decision made in the prior step. The analysis team will be fully unblinded for all remaining analysis.

E. Test Size and Confidence Levels

The type I error for the non-inferiority test and other performance outcomes will be set at the two-sided $\alpha=0.05$ significance level.

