As part of the blind analysis review, we will ascertain whether or not study outcomes differ for rural and urban sites. If they do not differ, as anticipated, we will combine the data from the five sites in Karachi with the five sites in Thatta. If differences are detected via descriptive analyses, we will present stratified results, but will be unable to test for significant differences as the trial was not powered for that purpose. In that event, the focus will be on the urban sites only, whose sample size (n=342) was powered to test the non-inferiority hypothesis.

Other comparisons between groups will be primarily descriptive to explore the differences in the provision of DMPA services and client satisfaction measures by each cadre of provider, by DMPA type and urban/rural setting if those data are not pooled. Similarly, objective and provider-perceived comparisons between injection techniques and injection characteristics, respectively, will be primarily descriptive and exploratory.

Analyses by Objective

Objective 1: *To assess whether LHWs can screen and initiate women on DMPA injections as safely and effectively as LHV.*

To answer this objective, the analysis will report the odds ratio of appropriate screening and counseling by LHWs compared with LHV using multi-level generalized mixed models as described above. The generalized linear mixed model accounts for the multilevel structure of the data (i.e., clinics and providers).

Objective 2: *Assess whether DMPA clients of Lady Health Workers and Lady Health Visitors are equally satisfied with their respective providers and the family planning services they provide.*

Descriptive analysis will be completed using indicators of client satisfaction and client-provider interactions for LHW and LHV clients.

Table 2: Summary of analysis approach and data sources for the primary and secondary outcomes

Outcome	Analysis	Stratified by	Source
Objective 1 Outcomes			
Screening for DMPA use	GLMM and descriptive	Cadre, urban/rural	Observation checklist of screening and gold-standard nurse's assessment
Counseling/Discussion of DMPA side effects, danger/warning signs, advantages and disadvantages	GLMM and descriptive	Cadre, urban/rural	Observation checklist of screening
Appropriate injection technique*	Descriptive	Cadre, urban/rural	Observation checklist for DMPA-IM, q1-q17; Observation checklist for DMPA-SP, q1-q22
Needle stick injuries*	Descriptive	Cadre, urban/rural	LHW/LHV questionnaire

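### The population for the primary non-inferiority test (pooled or urban-only) is chosen after outcomes by masked arm and setting are seen, with no stated size of difference and an inconsistent basis

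*SAP*

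**What the plan says.** SAP V.D (Blind Data Review) sets the order of events. Outcomes are first finalised and described by facility and by setting. Masked arm codes are then released, and "A descriptive bivariate analysis will be done using blinded treatment assignments stratified by rural/urban designation to assess whether pooling the data will be appropriate". Of the primary screening analysis it says: "This will be based on the pooled data or on the urban data only depending on the decision made in the prior step". SAP IV confirms the timing: "The decision whether to pool the data or not will be made during the blind review of the data as described below".

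The criterion is worded differently from place to place:

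- Protocol, Sample size (repeated in SAP IV): "If we can be comfortable that providers in rural and urban areas perform in similar manner", the data may be pooled. Both documents give the purpose of the rural sample as looking at LHV-LHW performance differences across settings.
- SAP V.D: whether pooling is appropriate, judged from the masked-arm table by setting.
- SAP VIII (Analytical model): "we will ascertain whether or not study outcomes differ for rural and urban sites". It continues: "If differences are detected via descriptive analyses, we will present stratified results, but will be unable to test for significant differences". The consequence follows: "In that event, the focus will be on the urban sites only, whose sample size (n=342) was powered to test the non-inferiority hypothesis".

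The Protocol's Sample size section also warns that "the additional sample size from rural areas will not be adequate for separate analyses by location or to assess rural and urban differences statistically".

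Several things are fixed in advance. Pooling is the anticipated result, urban-only is the named fallback, the decision precedes the primary test, and cadre labels stay masked until the primary conclusion has been verified.

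**The concern.** The confirmatory data set is selected from the outcome data by a standard that is not written down. Two teams with the same tables could reasonably test different populations. Masking hides which arm is LHW, but not whether the gap between the arms differs by setting, and that is what the step-two table displays. The choice also rests on a comparison that both documents say the sample cannot support statistically.

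What is at stake is the scope of the claim. A marked rural shortfall among LHWs would tend to move the confirmatory test to urban sites. Yet the Protocol (Risks and benefits) gives access for rural and underserved women as part of the trial's purpose.

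**Working it through.** **1. Inputs.** From the documents: 342 urban and about 100 rural clients, 1:1 allocation (171 and 50 per arm), 95% success in both cadres, margin 7.5 points, 90% power, 5% level. SAP V.E says two-sided 0.05, while the Table 1 shell carries both a 90% and a 95% CI. Results are therefore given at one-sided 5%, with one-sided 2.5% in brackets. My assumptions: a trigger size, because the SAP has none; a Wald test; no clustering. The planned mixed model is not simulated.

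**2. The plan's own figure.** With the score (Farrington-Manning) null variance, the restricted rates are 0.968 and 0.893:

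- s0 = √(0.968×0.032 + 0.893×0.107) = 0.355
- s1 = √(2×0.95×0.05) = 0.308
- n per arm = [(1.645×0.355 + 1.282×0.308)/0.075]² = 170.4, so 171 per arm and 342 in total

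The stated 342 reproduces at one-sided 5%. Power for a population fixed in advance is Φ[(0.075√n − z·s0)/s1]:

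- urban-only, n = 171 per arm: 90.1% [82.2%]
- all sites, n = 221 per arm: 95.8% [91.3%]

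**3. Ceiling on error.** The urban and pooled statistics have correlation √(342/442) = 0.88. If the more favourable data set were always used, a nominal 5% would become 7.0%, and 2.5% would become 3.6% (bivariate normal).

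**4. Chance of dropping rural data when nothing differs.** With 95% everywhere, the SE of (rural gap − urban gap) is √(2×0.0475/171 + 2×0.0475/50) = 0.0496. Triggers of 5, 10 and 15 points lie 1.01, 2.02 and 3.03 SEs from zero. Simulation gives 31%, 4% and 0.3% of trials.

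**5. Simulation.** 400,000 trials per scenario. The pooled estimate is weighted 171:50 with stratified variance. The rule is urban-only if the two settings' arm gaps differ by more than the trigger, otherwise pooled. Entries are the percentage of trials declaring non-inferiority.

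| Scenario | Always pooled | Always urban-only | 10-point trigger |
|---|---|---|---|
| LHW 7.5 points worse everywhere (false claim) | 5.7 [3.0] | 5.6 [3.0] | 6.5 [3.5] |
| No difference anywhere, 95% | 97.2 [94.9] | 93.6 [88.0] | 96.6 [94.1] |
| Urban equal, rural LHW 15 points worse | 55 [43] | 94 [88] | 90 [84] |

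In the first row the highest rate over triggers is about 6.8% [3.7%]. In the third row, triggers of 5 and 15 points give 93% and 81%, and the two data sets disagree in 39% of trials. There the true pooled deficit is 15×50/221 = 3.4 points, inside the margin, so the 55% is limited power and not a false claim for the pooled population.

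**6. Basis of the decision.** In the third scenario, a 10-point trigger on overall urban and rural rates (arms combined) gives 69% success, against 90% for the gap trigger. The basis does not always matter. With both cadres at 85% in rural sites, the two triggers drop rural data in 49% and 18% of trials, but success is 93.9% and 92.9%.

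**The case against.** The strongest defence has four parts.

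- **The basis is not wholly open.** The Protocol's Sample size section and SAP IV and V.D point to the LHW-LHV gap, and V.D ties the choice to the screening test. This stands. A reader might infer that no metric exists at all. The documents support less than that: SAP VIII is looser than the other sections, and no section gives a size.
- **Masking prevents choosing by known direction.** This also stands. A reader might infer that the team could knowingly select the favourable data set, but cadre labels stay masked through the primary conclusion. Masking does not stop the choice from depending on whether the gaps differ.
- **The large contrasts need an assumed rural deficit.** Nothing in the documents suggests a 15-point shortfall, and the plan expects none. With no true difference, a 10-point trigger costs about 0.6 points of success (97.2% against 96.6%).
- **Urban-only is not improvised.** The full target of 342 was placed in urban sites, and stratified results are promised if the settings differ. A reader might infer that rural results would be hidden. They would not be: the Table 4 shell shows rural screening by cadre, and the screening row of SAP Table 2 has no pooling asterisk. They would, however, fall outside the confirmatory test.

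**Conclusion.** The concern holds: the tested population depends on the outcome data, no size of difference is stated, and the basis is inconsistent between sections. It should be corrected, but it is not a serious threat to the error rate. A reader might infer substantial type I inflation. With a uniform deficit the increase is about 1 point (5.7% to at most about 6.8%; at one-sided 2.5%, about 3.0% to 3.7%). The larger movement, 55% pooled against 90% with a 10-point trigger, is a change of population under an assumed rural shortfall. It is not a type I error for the urban sites, where the cadres are equal in that scenario. All of these figures rest on assumed triggers, Wald tests and no clustering. Correlation within providers would make chance differences between settings more frequent.

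**What to change.** Before any outcome review, name one primary population and make the other a sensitivity analysis. Remove the outcome-based pooling decision from the Protocol's Sample size section and from SAP IV, V.D and VIII. Either choice is sound:

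- **All ten sites.** This is the analysis the SAP anticipates, with about 96% power at one-sided 5% without clustering. A pooled test can dilute a rural deficit.
- **Five urban sites.** This is the group sized for 90% power. Rural clients then fall outside the confirmatory test, and score-based power is about 82% if one-sided 2.5% is the intended level.

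Possible wording: *The primary non-inferiority test will include [all ten sites / the five urban sites], whatever the observed outcomes. The analysis in [the five urban sites / all ten sites] is a sensitivity analysis. Appropriate screening by cadre will always be reported separately for urban and rural sites.*

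For the by-setting report, give a descriptive risk difference with a CI from a named method that allows for clustering, for example standardised from the mixed model, because the planned model itself yields odds ratios. Replace the conditional pooling wording in SAP V.C (Counseling), SAP VIII and the Table 2 footnote with a fixed list of outcomes shown by setting.

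The cost is a wording amendment to both documents, with no extra clients. The rural interval will be wide: the 95% half-width is at least 1.96×√(2×0.95×0.05/50) = 8.5 points before clustering, so it should be labelled descriptive.

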**Primary Outcomes:**

- Proportion of Lady Health Workers and Lady Health Visitors that appropriately screen women for DMPA use;
- Proportion of Lady Health Worker and Lady Health Visitor clients that report discussion with their respective providers on side effects, danger signs, advantages and disadvantages of DMPA use;
- Proportion of Lady Health Workers and Lady Health Visitors that demonstrate appropriate injection technique
- Proportion of Lady Health Workers and Lady Health Visitors that report needle stick injuries;
- Proportion of Lady Health Workers that properly maintains a client (re)injection log.

**Secondary Objective:** To assess whether DMPA clients of Lady Health Workers and Lady Health Visitors are equally satisfied with their respective providers and the family planning services they provide.

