## **II. Objectives and Outcomes**

The overall goal of the trial is to provide high-level evidence that lay or community health workers can safely and effectively screen and initiate women who choose to use injectable contraceptives. The primary objective is:

To assess whether the community health worker cadre, Lady Health Workers (LHWs) in Pakistan can screen and initiate women on intramuscular and subcutaneous Depo Provera injections as safely and effectively as their clinically-trained counterparts, Lady Health Visitors (LHVs).

Although LHWs are already allowed to provide follow-up doses in the community, this RCT will focus on the comparison of safety and effectiveness of screening, counseling and first-time administration of DMPA IM and SP. Rather than focusing on determining whether services are better provided by one of the two health worker cadres, we want to determine if LHWs can perform just as well as the more experienced LHVs. Therefore, the trial will be powered specifically to detect non-inferiority (i.e., no difference) within a tolerance margin in the performance of LHWs compared to LHVs with regard to screening--the procedure that determines a woman's eligibility to receive DMPA. We consider the assessment of the screening for DMPA use as the primary outcome of interest for addressing the primary objective. However, in addition to screening, metrics for counseling and administration of DMPA will constitute the endpoints for the primary objective described below:

- Proportion of Lady Health Workers and Lady Health Visitors that appropriately screen women for DMPA use;
- Proportion of Lady Health Worker and Lady Health Visitor clients that report discussion with their respective providers on side effects, danger signs, advantages and disadvantages of DMPA use;
- Proportion of Lady Health Workers and Lady Health Visitors that demonstrate appropriate injection technique
- Proportion of Lady Health Workers and Lady Health Visitors that report needle stick injuries;
- Proportion of Lady Health Workers that properly maintains a client (re)injection log.

Details on analysis of these endpoints will be provided in a separate data analysis plan.

The secondary objective is:

To assess whether DMPA clients of Lady Health Workers and Lady Health Visitors are equally satisfied with their respective providers and the family planning services they provide.

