### Data analysis

We plan to compare a series of indicators of the performance of LHWs compared to LHV in the provision of injectable contraception services. Our primary outcome is related to the screening process. We will test the non-inferiority hypothesis that LHWs can screen potential DMPA clients for method initiation just as adequately as LHV with a non-inferiority margin of 7.5%. Given the relationship between LHWs and LHV within clinics, we plan to use a generalized mixed model using a logit link to account for the correlations of participant outcomes within providers and providers within clinics. Random effects will be included for clinics and providers within clinic. The non-inferiority test will be conducted at a 5% significance level. A similar approach will be used to compare other performance outcomes. No covariate adjustments are planned for the primary analyses. However, these may be included for exploratory analyses. If any, these will be specified in the detailed analysis plan prior to data analysis. Other comparisons between groups will be primarily descriptive to explore the differences in the provision of DMPA services by each cadre of provider. Similarly, comparisons between injection techniques will be primarily descriptive and exploratory.

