VI. Analysis of Fieldwork Data

An analysis of fieldwork data will be presented. This will include the number of DMPA acceptors approached, included, and randomized to LHW or LHV care.

VII. Analysis of participant characteristics

A descriptive summary of DMPA user, LHV, and LHW characteristics will be presented by urban and rural setting. DMPA client characteristics will include age, marital status, education, number of children, desire for more children, and birth spacing plans. Provider characteristics will include age, marital status, education, years of service, and years of DMPA experience.

VIII. Analysis of Study Objectives

We plan to compare a series of indicators of the performance of LHWs compared to LHVs in the provision of injectable contraception services. Our primary outcome, appropriate screening, is a binary variable comprised of the gold standard nurse's assessment of client eligibility for DMPA compared with the LHV's or LHW's assessment of client eligibility. If the LHV's or LHW's assessment agrees with the gold standard nurse's assessment, the screening is deemed appropriate.

Analytical model

We will test the non-inferiority hypothesis that LHWs can screen potential DMPA clients for method initiation just as adequately as LHV with a non-inferiority margin of 7.5%. Given the relationship between LHWs and LHV within clinics, we will employ a generalized mixed model using a logit link to account for the correlations of participant outcomes within providers and providers within clinics. Random effects will be included for clinics and providers within clinic. The non-inferiority test will be conducted at a 5% significance level. A similar approach will be used to compare appropriate counseling. No covariate adjustments are planned for the primary analyses. However, exploratory analyses will include the following covariates: LHV/LHW age, marital status, education level, years of service, years of experience with DMPA, and average DMPA-IM injections given per month prior to the trial. Years of service, years of experience with DMPA, and average injections per month will be analyzed either as categorical or continuous variables based on exploratory analyses; either odds ratios or beta coefficients will be reported.

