Appropriate counseling defined as having discussed side effects, warning/danger signs, advantages, and disadvantages of DMPA				

Table 4: Comparison of Lady Health Workers and Lady Health Visitors on DMPA service delivery indicators (n, %)

	Urban	Rural		
	LHW	LHV	LHW	LHV
Appropriate screening				
Appropriate counseling				
side effects				
danger signs				
advantages/disadvantages				
Appropriate injection technique				
Needle stick injuries				
Client log maintained				

Objective 2: Client Satisfaction and Client-Provider Interaction

Table 5: Exemplar of Client Satisfaction and Client-Provider Interaction items (n, %)

	LHW		LHV	
	SP	IM	SP	IM
Satisfaction with method				
very satisfied				
somewhat satisfied				
not satisfied				
Satisfaction with services				
very satisfied				
somewhat satisfied				
not satisfied				
Satisfaction with provider				
very satisfied				
somewhat satisfied				
not satisfied				
Comfort asking questions				
yes				
no				

Figure 1: Graphic presentation of observation checklist for screening

Observation Checklist to Evaluate Providers Who Screen Clients for Initial DMPA Use

Type of provider being observed: Lady Health Worker
Lady Health Visitor

Please record the response given to the provider by the client for the following items. If the provider does not ask the question, please draw a line through the item.

NO	1. Have you ever been told you have breast cancer?	YES
NO	2. Have you ever had a stroke or heart attack, or do you currently have a blood clot in your legs or lungs?	YES
NO	3. Do you have a serious liver disease or jaundice (yellow skin or eyes)?	YES
NO	4. Have you ever been told you have diabetes (high sugar in your blood)?	YES
NO	5. Have you ever been told you have high blood pressure?	YES
NO	6. Do you have bleeding between menstrual periods, which is unusual for you, or bleeding after intercourse (sex)?	YES
NO	7. Have you ever been told that you have a rheumatic disease such as lupus?	YES
NO	8. Do you have two or more conditions that could increase your chances of a heart attack or stroke, such as smoking, obesity, high blood pressure, or diabetes?	YES
NO	9. Are you currently breastfeeding a baby less than 6 weeks old?	YES

If the client answered NO to *all of questions 1–9*, did the provider tell her she is a good candidate for DMPA?
Yes No
Did provider proceed to questions 10–15?
Yes No

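### Injection technique is a listed primary outcome, but the SAP reports it as n (%) only, so the administration part of Objective 1 has no planned between-cadre estimate, interval or allowance for provider clustering

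*SAP*

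**What the plan says.** Both documents list five primary outcomes. One of them is "Proportion of Lady Health Workers and Lady Health Visitors that demonstrate appropriate injection technique". Protocol section II ranks screening first ("We consider the assessment of the screening for DMPA use as the primary outcome of interest for addressing the primary objective") and powers the trial on it alone. It then adds that "metrics for counseling and administration of DMPA will constitute the endpoints for the primary objective described below".

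Protocol section IV, Data analysis, describes a logit mixed model with random effects for clinic and for provider within clinic, ties it to the screening non-inferiority test, and continues: "A similar approach will be used to compare other performance outcomes". Later in that paragraph it makes the remaining group comparisons mainly descriptive.

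SAP section VIII, Analytical model, repeats the model, but its matching sentence is "A similar approach will be used to compare appropriate counseling". Section VIII then says "Other comparisons between groups will be primarily descriptive to explore the differences in the provision of DMPA services", and under Objective 1 it promises odds ratios for screening and counselling. SAP Table 2 assigns a GLMM to those two outcomes and marks technique, needle sticks and the log as descriptive. The Table 1 shell has rows for screening and counselling only. The Table 4 shell has no column for a difference, an interval or a p-value.

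SAP section V.E nevertheless reads "The type I error for the non-inferiority test and other performance outcomes will be set at the two-sided" 0.05 level.

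SAP section V.C makes technique a pass/fail composite: at least 18 of 22 checklist items for SP and at least 14 of 17 for IM.

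**The concern.** Objective 1 covers initiating women on the method as well as screening them, and initiating includes giving the injection. Of the five listed outcomes, technique is the only one in which that act is observed. Needle sticks are reported by the provider at an interview months later.

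Under the SAP, a reader will see two percentages per setting. These show the direction of any gap, but not how large a deficit among Lady Health Workers (LHWs) the data leave open. They also treat injections by the same provider as independent, although the urban sample rests on five Lady Health Visitors (LHVs). The SAP gives no reason for modelling counselling and not technique.

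**Working it through.** **1. The plan's own figure.** The only sample size is for screening: 342, with 95% success in both arms, a 7.5-point margin and 90% power. With one-sided 0.05,

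n = 2p(1−p)(z₀.₉₅ + z₀.₉₀)²/δ² = 2 × 0.95 × 0.05 × (1.645 + 1.282)²/0.075² ≈ 144.6.

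The continuity correction gives (n/4)[1 + √(1 + 4/(nδ))]² ≈ 170.3, so 171 per arm and 342 in total. The figure reproduces. No rate, margin, ICC or power is stated for technique, so 171 per urban arm is only a ceiling on the injections that can be observed.

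**2. What the Protocol's phrase can cover.** The four listed outcomes other than screening compare as follows:

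| Outcome | LHV comparator? | Recorded per client? | SAP Table 2 |
|---|---|---|---|
| Counselling | yes | yes | GLMM and descriptive |
| Injection technique | yes | yes | Descriptive |
| Needle sticks | yes | no, per provider (30 v 10) | Descriptive |
| (Re)injection log | no, LHWs only | no | Descriptive |

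The client-level model fits counselling and technique. It does not fit the log, and needle sticks are counted per provider. The Protocol's plural, and the plural kept in SAP V.E, are most naturally read as covering both client-level outcomes. Counselling has no margin or power either and is still modelled, so lack of power does not explain the difference.

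**3. Precision available.** Assumptions: about 160 observed injections per urban arm (94% of 171, because only clients whom the nurse finds eligible are injected) and equal rates p. Unclustered 95% half-width = 1.96 × √(2p(1−p)/n):

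- p = 0.90, n = 160: 1.96 × √(0.18/160) = 6.6 points
- p = 0.85, n = 160: 7.8 points
- p = 0.90, n = 210 per arm (pooled; 95% of 221): 5.7 points

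**4. Provider clustering.** With three LHWs and one LHV at each of five urban sites, 160 injections per arm means about 10.7 per LHW (15 providers) and 32 per LHV (5 providers). Design effect = 1 + (m − 1) × ICC in each arm. Half-width = 1.96 × √(p(1−p)/n × (DE_LHW + DE_LHV)), at p = 0.90:

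| Assumed provider ICC | DE, LHW | DE, LHV | Half-width |
|---|---|---|---|
| 0 | 1 | 1 | 6.6 |
| 0.01 | 1.10 | 1.31 | 7.2 |
| 0.05 | 1.48 | 2.55 | 9.3 |
| 0.10 | 1.97 | 4.10 | 11.4 |

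This ignores any gain from comparing cadres within the same clinic.

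**5. Against screening.** At the planned 95% rate and 171 per arm, the unclustered half-width for screening is 1.96 × √(2 × 0.95 × 0.05/171) = 4.6 points.

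**The case against.** The strongest reply is that the SAP was entitled to choose. The Protocol never names technique for the mixed model. It defers the analysis of these endpoints to a separate plan, and its own paragraph has the same sentence making other comparisons mainly descriptive. The phrase about other performance outcomes cannot mean every listed outcome, since the log has no LHV arm. The type I error statement in SAP V.E could refer to counselling alone. The Protocol introduction says that the missing evidence concerns screening and counselling of first-time users, and that LHWs may already give follow-up IM doses unsupervised.

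Much of this stands. That technique belongs with the modelled outcomes is the most natural reading, not an explicit commitment, and the SAP may narrow the analysis if it says why. The introduction does not settle the matter: it credits only some LHWs with proven technique, and for IM, while the Protocol says that SP is new to both cadres. Nor is it given as the reason for the SAP's choice.

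The statements that comparisons between injection techniques are exploratory do not answer the point. They concern IM against SP, not LHW against LHV.

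A reader might infer that the safety half of the objective gets no inference at all. The documents do not support that. Protocol section II and SAP section I attach safety and effectiveness to screening, counselling and administration together. Screening has the non-inferiority test, and counselling, which includes danger signs, has the mixed model.

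**Conclusion.** The point holds as a gap in reporting and a mismatch between passages. A listed primary outcome, recorded per client and compared between cadres, gets percentages alone, while counselling, equally unpowered, gets a model. The Protocol's Data analysis section and SAP V.E do not sit easily with the SAP's Analytical model and Table 2.

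Under the assumptions above, the unreported uncertainty is about ±6.6 points unclustered and about ±9 to ±11 points at a provider ICC of 0.05 to 0.10. The counts, rates and ICCs are all assumed, because the documents give none for technique.

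Two further inferences should be resisted. One is that technique would be estimated about as precisely as screening: ±6.6 is already about 1.4 times the 4.6 points for screening, and plausible clustering widens it past the 7.5-point screening margin. The other is that a non-inferiority test is owed: no margin or power is set for this outcome, and the screening margin cannot simply be borrowed.

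**What to change.** - In SAP Table 2, change the injection technique entry to *GLMM and descriptive*, and state that the unit is the observed injection, since the outcome is worded per provider.
- Fit the clinic and provider-within-clinic model already planned for counselling. The two checklists differ, so either include DMPA type (IM or SP) as a term, stated as an exception to the no-covariate rule, or also show results by type.
- Add a technique row to the Table 1 shell with the odds ratio and its interval. That shell heads its column 90% while its footnote says 95%, so state the level. Also report the model-standardised LHW minus LHV risk difference with a clustering-adjusted interval.
- State that the analysis covers clients who received an injection, a subset formed after randomisation, and that no non-inferiority claim will be made.
- Bring the Protocol's Data analysis section, SAP V.E, the SAP's Analytical model and Table 2 into agreement on which outcomes are modelled. If technique is to stay descriptive, give the reason.

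The cost is SAP wording, one more model on data already collected, and a standardisation step, because a logit model does not give a risk difference directly. With five urban LHVs the interval will probably be wide and will look less favourable than bare percentages. No extra sample is needed.
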